Endpoints for conditional secondary objectives #1 and #2:

- Individual serum neutralizing titer at D01 and D15 against the B.1.351 variant for the CoV2 preS dTM-AS03 (B.1.351) vaccine and the CoV2 preS dTM-AS03 (D614 + B.1.351) vaccine Intervention Groups.
- Individual serum neutralizing titer at D01 and D15 against the D614G strain for the CoV2 preS dTM-AS03 (D614 + B.1.351) vaccine Intervention Group.
- Individual serum neutralizing titer against the D614 strain at D36 (Comparator Group)

Endpoints for conditional secondary objectives #3:

- Individual serum neutralizing titer at D15 against the B.1.351 variant for the CoV2 preS dTM-AS03 (B.1.351) vaccine and the CoV2 preS dTM-AS03 (D614 + B.1.351) vaccine Intervention Groups
- Individual serum neutralizing titer at D36 against the B.1.351 variant for the Comparator Group

Endpoints for secondary objectives #4 - #5:

- Seroresponse rate, defined as a 4-fold or greater rise in serum neutralization titer [post/pre] at D15 relative to

Conditional secondary objective: conditional on meeting the primary immunogenicity objectives (1) and (2) and the co-secondary objectives for Supplemental Cohort 2:

- 3) To demonstrate in adults 18-55 years of age and previously vaccinated with the Pfizer/BioNTech vaccine, that a booster dose of CoV2 preS dTM-AS03 (B.1.351) vaccine or CoV2 preS dTM-AS03 (D614 + B.1.351) vaccine induces an immune response against the B.1.351 variant at D15 that is superior to that against the B.1.351 variant at D36 in the Comparator Group.

Conditional secondary objectives: conditional on meeting the conditional secondary objective (3) for Supplemental Cohort 2, the following objectives will be sequentially tested:

- 4) To demonstrate in adults 18-55 years of age and previously vaccinated with the Pfizer/BioNTech vaccine that a booster dose of CoV2 preS dTM-AS03 (B.1.351) vaccine or CoV2 preS dTM-AS03 (D614 + B.1.351) vaccine induces a seroresponse that is non-inferior to the seroresponse induced by a two-dose priming series with the CoV2 preS dTM-AS03 (D614) vaccine in naïve, previously unvaccinated individuals.

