3) To demonstrate in adults 18-55 years of age and previously vaccinated with an mRNA COVID-19 vaccine, that a booster dose of CoV2 preS dTM-AS03 (D614) vaccine induces an immune response that is non-inferior to the response induced by a two-dose priming series with CoV2 preS dTM-AS03 (D614) vaccine in naïve, previously unvaccinated individuals.	Endpoints for secondary objectives #11 - #14: 
• Individual serum neutralizing titer at D01 and D15 against the D614G strain in each Intervention Group• Individual serum neutralization titer fold-rise post-vaccination relative to D01 at D15 against the D614G strain in each Intervention Group• \geq 2-fold-rise and \geq 4-fold-rise in serum neutralization titer [post/pre] (fold-rise \geq 2 and \geq 4) at D15 relative to D01 against the D614G strain in each study Intervention Group• Seroresponse rate, defined as a 4-fold or greater rise in serum neutralization titer [post/pre] at D15 relative to D01, against the D614G strain in each study Intervention Group
4) To demonstrate in adults 18-55 years of age and previously vaccinated with an mRNA COVID-19 vaccine, that a booster dose of CoV2 preS dTM-AS03 (D614) vaccine induces an immune response that is superior to that observed immediately before booster.	Endpoints for secondary objective #15: 
• Individual serum neutralizing titer at D01 and D15 to the B.1.351 variant in each Intervention Group• Individual serum neutralizing titer at D01 and D36 to B.1.351 variant in the Comparator Group
Conditional secondary objectives: conditional on meeting the conditional secondary objectives (3) and (4) for Supplemental Cohort 1:	
5) To demonstrate, in adults 18-55 years of age previously vaccinated with an adenovirus-vectored COVID-19 vaccine, that a booster dose of CoV2 preS dTM-AS03 (D614) vaccine induces an immune response that is non-inferior to the response induced by a two-dose priming series with CoV2 preS dTM-AS03 (D614) vaccine in naïve, previously unvaccinated, individuals.	

6) To demonstrate, in adults 18-55 years of age previously vaccinated with adenovirus-vectorized COVID-19 vaccines, that a booster dose of CoV2 preS dTM-AS03 (D614) vaccine induces an immune response that is superior to that observed immediately before booster.

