
Oxford/AstraZeneca vaccine, the immune response to a booster dose of CoV2 preS dTM-AS03 (D614) vaccine.
 
13) To describe, in adults 18-55 years of age previously vaccinated with the J&J/Janssen vaccine, the immune response to a booster dose of CoV2 preS dTM-AS03 (D614) vaccine.
 
14) To describe, in adults 18-55 years of age previously vaccinated with any COVID-19 vaccine, the immune response to a booster dose of CoV2 preS dTM-AS03 (D614) vaccine.
 
15) To compare the neutralizing antibody profile to the B.1.351 variant at D01 and D15 in the booster groups and at D36 in the Comparator group.
 
16) To compare the neutralizing antibody profile to the B.1.351 variant at D01 and D15 in the booster groups and neutralizing antibody profile to the D614G strain at D36 in the Comparator Group.
 
17) To assess the neutralizing antibody profile to the D614G strain and to the B.1.351 variant at D29, D91, D181, and D366 overall, and by age group, by priming platform, and by priming vaccine.
 
18) To describe the neutralizing antibody profile to the B.1.351 variant and to the D614G strain at D01 and D15 in adults older than 55 years of age in the booster group, overall, by priming platform, and by priming vaccine.
 
19) To assess the binding antibody profile at D01, D15, D29, D91, D181, and D366 after booster immunization in adults previously vaccinated with COVID-19 vaccines, overall and by age group, by priming platform, and by priming vaccine.
	
 Responders, defined as participants who had baseline values below LLOQ with quantifiable antibody concentration above assay LLOQ at pre-defined post-vaccination timepoints and participants with baseline values above LLOQ with a 4-fold increase in binding antibody concentration at each pre-defined post-vaccination timepoint

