Eligible participants transitioning from the VAT00002 Original Phase II Cohort who have received the CoV2 preS dTM-AS03 (D614) candidate vaccine (targeted N = 450; actual number to be determined by number of VAT00002 participants meeting eligibility criteria for transition) will be randomized to receive a single injection of either the CoV2 preS dTM-AS03 (D614) or the CoV2 preS dTM-AS03 (B.1.351) booster vaccine. Randomization will occur by age strata (assumption that about 2/3 of participants will be 18-55 years of age (ie, 300 adults 18-55 years old, allocation ratio of 9:1 between CoV2 preS dTM-AS03 [D614] group and the CoV2 preS dTM-AS03 [B.1.351] group); the actual number and age distribution will be determined by characteristics of those who meet eligibility criteria for transition). A subset of 10% of participants aged 18-55 (~30 participants in the 2 Booster Groups combined) will be randomly assigned to collect CMI and mucosal samples plus variant testing.

Site staff will connect to the IRT system, enter the identification and security information, and confirm a minimal amount of data in response to IRT prompts. The IRT will collect information on age-group, priming vaccine, high-risk medical conditions, and ethnicity/race (the last 2 for monitoring purposes and high-risk medical conditions for potential capping). The IRT will then provide the group assignment (intervention arm and CMI/mucosal subset [if applicable]). The full detailed procedures for group allocation are described in the Operating Guidelines.

Supplemental Cohorts Comparator Group:

This Group will be open-label and not randomly assigned as all eligible participants will have common baseline characteristics (previously unvaccinated) and all will receive two injections of the CoV2 preS dTM-AS03 (D614) candidate vaccine 21 days apart. Eligible participants must be 18-55 years of age and have a negative baseline SARS-CoV-2 rapid serodiagnostic test to be enrolled into this group. A subset of 5% of participants aged 18-55 (~26 participants) will be randomly assigned to variant testing subsets.

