This assay will be used to measure neutralizing antibody responses to the prototype strain (D614G variant) at all timepoints in all participants (all Cohorts). The neutralizing antibody response to the emerging variant B.1.351 will also be performed at D36 in the Original Phase II Cohort and all timepoints in Supplemental Cohort 2.

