For the CoV2 preS dTM-AS03 (B.1.351) booster candidate, there are 2 co-primary endpoints to be hypotheses tested at 0.025/3 one-sided level in participants primed with the Pfizer/BioNTech vaccine. If the primary objectives are met, then 2 conditional secondary endpoints will be hypotheses tested at 0.025/3 one-side level in participants primed with an mRNA vaccine applying the sequential testing strategy. If primary objectives and conditional secondary objectives are both met, then 1 conditional secondary endpoint (GMT) will be hypothesis tested with one-sided alpha 0.025/3 in participants primed with the Pfizer/BioNTech vaccine applying the sequential testing strategy. If the primary objectives, conditional secondary objectives, and conditional secondary objective on GMT are all met, then 1 conditional secondary endpoint on

seroresponse will be hypothesis tested at one-sided alpha 0.025/3 in each Pfizer/BioNTech primed and mRNA primed sequentially by applying the sequential testing strategy.

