Alternative hypothesis (H_1) : Ratio $(\text{post-booster}/\text{pre-booster}) > 2$

Each of the 2 Booster Groups, CoV2 preS dTM-AS03 (B.1.351) or CoV2 preS dTM-AS03 (D614 + B.1.351), will be tested separately. The superiority will be demonstrated for either or both of the Booster Groups(s) if the lower limit of the two-sided 98.3% CI of the ratio of serum neutralization titer is great than 2.

For each of the Booster Groups, the conditional secondary objective will be reached if both non-inferiority and superiority testing described above are demonstrated. For CoV2 preS dTM-AS03 (D614 + B.1.351), the approach is used across strains (B.1.351 and D614) (if the SARS-CoV-2 D614G variant remains in circulation globally based on reports from authorities [eg, WHO]) or only on the B.1.351 variant.

If the primary immunogenicity objective in participants primed with the Pfizer/BioNTech vaccine and conditional secondary immunogenicity objectives for participants primed with an mRNA vaccine are both achieved, then 1 conditional secondary endpoint on GMT for CoV2 preS dTM-AS03 (B.1.351) or CoV2 preS dTM-AS03 (D614 + B.1.351), will be tested separately.

Conditional secondary objective 2: superiority to the comparator in terms of GMT against B.1.351:

For participants, 18-55 years of age, primed with the Pfizer/BioNTech vaccine, 14 days after the booster dose (ie, D15) of CoV2 preS dTM-AS03 (B.1.351) (non-exploratory arm only) or CoV2 preS dTM-AS03 (D614 + B.1.351), GMT against B.1.351 of CoV2 preS dTM-AS03 (B.1.351) or/and CoV2 preS dTM-AS03 (D614 + B.1.351) is superior to the GMT against B.1.351 of the primary vaccination Comparator Group.

Null hypothesis (H_0) : $\text{GMT}_{(\text{variant})} / \text{GMT}_{(\text{comparator})} \leq 1.5$

Alternative hypothesis (H_1) : $\text{GMT}_{(\text{variant})} / \text{GMT}_{(\text{comparator})} > 1.5$

Each of the 2 variant-containing vaccine groups, CoV2 preS dTM-AS03 (B.1.351) or CoV2 preS dTM-AS03 (D614 + B.1.351), will be tested separately. The superiority will be demonstrated if the lower limit of the two-sided 98.3% CI of the ratio of the GMT is greater than 1.5 for each or both variant-containing vaccine group(s).

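### Section 8.2.1.1 omits the Comparator Group and Cohort 1 from B.1.351 neutralization testing that the objectives, a gating superiority hypothesis and the power table require

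*Protocol*

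**What the plan says.** Section 8.2.1.1 sets the scope of the primary neutralization assay by strain. For D614G it covers the "prototype strain (D614G variant) at all timepoints in all participants (all Cohorts". For B.1.351, testing of "variant B.1.351 will also be performed at D36 in the Original Phase II Cohort and all timepoints in Supplemental Cohort 2" is planned. The Comparator Group and Cohort 1 are not named.

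Other sections rely on B.1.351 titres in those two groups:

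- **Cohort 2, conditional secondary objective 3** (Synopsis and Table 3.1; numbered conditional secondary objective 2 in Section 9.1.2.3). The control endpoint is "Individual serum neutralizing titer at D36 against the B.1.351 variant for the Comparator Group". The hypothesis is that the booster GMT against B.1.351 "is superior to the GMT against B.1.351 of the primary vaccination Comparator Group".
- **Gating** (Section 9.1.2). "If the primary objectives, conditional secondary objectives, and conditional secondary objective on GMT are all met, then 1 conditional secondary endpoint on" seroresponse is tested, first in Pfizer/BioNTech-primed and then in mRNA-primed participants. The bivalent candidate follows the same order.
- **Power** (Table 9.1). The superiority step is powered on Comparator GMT against B.1.351, at more than 99.9% for each Cohort 2 candidate.
- **Cohort 1, secondary objective 15** (Table 3.1). "To compare the neutralizing antibody profile to the B.1.351 variant at D01 and D15 in the booster groups and at D36" in the Comparator Group, with the endpoint "Individual serum neutralizing titer at D01 and D36 to B.1.351 variant in the Comparator Group".
- **Cohort 1, secondary objectives 16 to 18.** These need B.1.351 titres in the booster groups: D01 and D15 for objectives 16 and 18, and D29, D91, D181 and D366 for objective 17.

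For variant testing in the Comparator Group, Section 6.3.1 says: "A subset of 5% of participants aged 18-55 (~26 participants) will be randomly assigned to variant testing subsets".

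**The concern.** The section that says which groups are assayed against which strain does not match the sections that say which titres will be analysed. Read literally, it gives the Cohort 2 boosters B.1.351 titres but assigns none to the group they are to be compared with, and none to Cohort 1.

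The affected Cohort 2 comparison is a formal hypothesis in the fixed sequence, and the seroresponse tests for both Cohort 2 candidates come after it. If it were run on too few controls, those later tests would probably be closed off for a reason unrelated to the vaccines. For Cohort 1 the stake is smaller: descriptive secondary objectives without an assigned assay.

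**Working it through.** **1. Can other text supply the missing scope?**

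- *Opening line of Section 8.2.1.1.* It says the testing is done in all participants at all timepoints but names no strain. The strain-specific sentences that follow are more specific and treat D614G and B.1.351 differently.
- *Table 8.3 (Comparator).* A Variants of Concern row is marked at D01, D36, D202 and D387. It does not name B.1.351 or say whether it covers everyone or the subset.
- *Table 8.2 (boosters, including Cohort 1).* The corresponding row is marked at D01, D15, D29, D181 and D366 and is blank at D91. Section 8.2.1.1 promises B.1.351 at all Cohort 2 timepoints, and Cohort 1 objective 17 and Cohort 2 objective 16 need D91. This row therefore cannot be the full B.1.351 schedule.
- *Subset text (Synopsis, Section 4.1.2, Table 4.5, Section 6.3.1).* Variant testing is described there as covering additional variants in randomized subsets, with about 26 Comparator participants.

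None of these states that B.1.351 is run in all Comparator participants or in Cohort 1.

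**2. Inputs for power** (Section 9.2.2, Table 9.1)

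- One-sided alpha: 0.025/3 = 0.00833.
- SD on the log10 scale: booster 1.0, comparator 0.65.
- Margin 1.5, assumed true ratio 3, so the effect is log10(3/1.5) = 0.301.
- Evaluable booster: 515 × 0.97 ≈ 500. Evaluable comparator: 515 × 0.90 ≈ 464, the figure also used in Section 9.1.2.1.

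**3. Formula.** Welch two-sample t-test with noncentrality 0.301 / √(1.0²/n_b + 0.65²/n_c). As a check, normal-approximation power is Φ(noncentrality − 2.394).

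**4. Reproducing the plan's figures.** With 500 and 464, the standard error is √(0.00200 + 0.00091) = 0.0540, the noncentrality is 5.58 and power is 99.9% (99.93% before rounding; plan: > 99.9%). The same set-up gives 80.5-80.6% for the Pfizer-primed B.1.351 non-inferiority test (plan: 80.5%) and 84.5-84.6% for mRNA-primed (plan: 84.5%). The method matches the plan's.

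**5. Superiority power by number of Comparator participants with a B.1.351 titre** (500 boosters)

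- 464: 99.9%.
- 130: 95.9% (illustrative).
- 26: standard error √(0.00200 + 0.01625) = 0.135, noncentrality 2.23, power 39% (normal approximation 43%).
- 23 (26 × 0.90): standard error √(0.00200 + 0.01837) = 0.143, noncentrality 2.11, power 35% (normal approximation 39%).
- None: the hypothesis cannot be tested.

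**The case against.** The strongest reply is that the protocol, taken as a whole, plainly intends these data. The B.1.351 sentence does not say *only*. The endpoints ask for Comparator B.1.351 titres in terms, and Table 8.3 marks variant neutralization at D36 with no subset flag on that row. Some headings and criteria speak of a Cohort 2 Comparator Group (Section 9.1.2.1, E03, E15), so Supplemental Cohort 2 might be read to include its comparator. B.1.351 has its own formal endpoints, so it is naturally not one of the additional variants reserved for the subset. Operating Guidelines and laboratory manuals may also spell the scope out.

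Much of this stands. A reader might infer that the superiority test has no control data and cannot be run. The documents do not support that: they contain a contradiction about assay scope, not a decision to leave the controls untested. Likewise, the 35-39% power belongs to one possible reading, and no section says that Comparator B.1.351 testing stops at 26 people. A reader might also suppose that all of Cohort 1 objectives 15 to 18 need Comparator B.1.351 titres. Only objective 15 does: objective 16 uses Comparator D614G titres, and 17 and 18 concern the booster groups.

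The reply does not remove the conflict. The Comparator is named throughout as a separate group shared by both cohorts, and Tables 4.5 and 6.2 list it under Cohort 1. Even the generous reading leaves out Cohort 1's 565 participants. Pooling in Phase II participants, who do have D36 B.1.351 testing, is a contingency for a substantial enrolment shortfall and assigns no assay to the 515 planned controls. Retained serum (Section 8.11) would allow a late repair, so any harm is recoverable, but that is no reason to leave the text as it is.

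**Conclusion.** The point holds as an internal contradiction. Section 8.2.1.1 names two groups for B.1.351 testing, while the endpoints, the superiority hypothesis and Table 9.1 need two more. The Variants of Concern rows do not settle which prevails.

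The size depends on how the gap is filled. With essentially the whole Comparator Group tested (about 464 evaluable), the stated power of more than 99.9% is right. With only the variant subset, it would be about 35-39%, under the plan's own assumptions of a true ratio of 3 and SDs of 1.0 and 0.65. What is exposed is the Cohort 2 superiority step, the seroresponse tests behind it, and the B.1.351 descriptive objectives of Cohort 1. The primary and co-secondary GMT tests compare against Comparator D614G titres, which Section 8.2.1.1 covers in full, and are not affected.

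**What to change.** Amend Section 8.2.1.1 to state that B.1.351 neutralization is run in all Comparator Group participants at D01 and D36, and in Cohort 1 at D01, D15, D29, D91, D181 and D366, alongside the scope already given for the Original Phase II Cohort and Cohort 2. In Tables 8.2 and 8.3, list B.1.351 as an all-participants assay with its own visit marks (including D91 in Table 8.2), separate from the additional variants tested only in the subsets.

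The cost is a wording change plus the assay runs. Blood is already drawn from all participants at these visits and the endpoints already call for the titres, so no visit or sample is added and no hypothesis, margin or sample size changes.

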8.2.2 Secondary Immunogenicity Assays

8.2.2.1 SARS-CoV-2 Neutralizing Antibody Assessment (SP)

SARS-CoV-2 neutralizing antibodies will be measured using a live virus neutralization assay in all participants included in the Original Phase II Cohort at all timepoints. This testing will be performed in the Original Phase II Cohort.

Serum samples are mixed with constant concentration of the SARS-CoV-2 virus. A reduction in virus infectivity (viral antigen production) due to neutralization by antibody present in serum samples can be detected by ELISA. After washing and fixation, SARS-CoV-2 antigen production in cells can be detected by successive incubations with an anti-SARS-CoV-2-specific antibody, HRP IgG conjugate, and a chromogenic substrate. The resulting optical density is measured using a microplate reader. The reduction in SARS-CoV-2 infectivity as compared to that in the virus control wells constitutes a positive neutralization reaction indicating the presence of neutralizing antibodies in the serum sample.

8.2.2.2 Detection of binding antibody levels by ECLIA

SARS-CoV-2 binding antibodies will be measured using an electrochemiluminescence immunoassay (ECLIA) in participants included in the Original Phase II Cohort at D36 and on D01 and D29 samples in all participants belonging to any groups evaluating priming vaccines (Cohort 1, Cohort 2 Main Arm, Cohort 2 Exploratory B.1.351 Arm).

The 4-plex SARS-CoV-2 assay (detecting serum IgG binding to SARS-CoV-2 antigens S Protein [S-2P], Receptor Binding Domain [RBD], and Nucleocapsid [N], with a Bovine Serum Albumin [BSA] control) is intended for use to aid in identifying volunteers with an immune response to SARS-CoV-2 S-2P after vaccination with experimental SARS-CoV-2 vaccines.

MSD SECTOR® plates are precoated by MSD with SARS-CoV-2 S-2P, RBD protein, N protein, and a BSA control in each well in a specific spot-designation for each antigen. The assay will be performed with a Beckman Coulter Biomek based automation integration platform including the Biotek 405TS Plate Washer. Serum samples will be heat-inactivated for 30 minutes at 56oC prior to assay. Plates are blocked for 60 minutes at room temperature (RT) with MSD blocker A solution without shaking. Plates are washed and MSD reference standard (calibrator), QC test sample (pool of COVID-19 convalescent sera) and human serum test samples are added to the precoated wells in duplicates in an 8-point dilution series. Reference standard is added in triplicates. MSD Control sera (low, medium, and high) are added undiluted in triplicates as per validated assay format. Additional assay controls might be added in triplicates. Samples are incubated at RT for 4 hours with shaking on a Titramax Plate shaker (Heidolph) at 1500 rpm. SARS-CoV-2 specific antibodies present in the sera or controls bind to the coated antigens. Plates

are washed to remove unbound antibodies. Antibodies bound to the SARS-CoV-2 viral proteins are detected using an MSD SULFO-TAGTM anti-human IgG detection antibody incubated for 60 minutes at RT and with shaking. Plates are washed and a read solution (MSD GOLDTM read buffer) containing electrochemiluminescence (ECL) substrate is applied to the wells, and the plate is entered into the MSD MESO Sector S 600 detection system. An electric current is applied to the plates and areas of well surface which form antigen-anti human IgG antibody SULFO-TAGTM complex will emit light in the presence of the ECL substrate.

The MSD MESO Sector S 600 detection system quantitates the amount of light emitted and reports the ECL unit response as a result for each test sample, control sample and reference standard of each plate. Analysis is performed with the MSD Discovery Workbench software, Version 4.0. Calculated ECLIA parameters to measure binding antibody activities will include interpolated concentrations or assigned international units (IU/mL) read from the standard curve.

